**4.2.3 When potential subjects will be recruited.**

We will recruit no more than 520 subjects in order to reach the randomization target of 290 subjects. We expect to reach this target by randomizing 36 subjects by month 30, 72 subjects by month 36, 120 subjects by month 42, 174 subjects by month 48, 230 subjects by month 54, and at least 290 subjects (but no more than 320 subjects) by month 60.

**4.2.4 Describe the eligibility screening process and indicate whether the screening process will occur before or after obtaining informed consent. Screening begins when the investigator obtains information about or from a prospective participant in order to determine their eligibility. In some studies, these procedures may not take place unless HIPAA Authorization is obtained OR a waiver of HIPAA Authorization when applicable for the screening procedures is approved by the IRB. [For FDA regulated studies, consent for any screening activities would need to be obtained prior to screening unless specifically waived by the IRB.]**

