#### **7.2.4 Randomization and Study Intervention**

Randomization is a critical feature of a clinical trial because it prevents treatment-selection biases. Subjects will be randomized after obtaining their baseline measurements and within 1 week before the start of the study intervention (Orientation). It is anticipated that the amount

of time between randomization and the start of the study intervention (Orientation) will be no more than 1 week. There will be rolling enrollment. We will run a new cohort of MBSR and SME control classes approximately every 3 months. Subjects will only be randomized to a cohort if they indicate they are available for the intervention classes for that cohort.

Two hundred ninety (290) adults with uncontrolled diabetes will be randomized with equal allocation to one of two study groups for 6 months: (1) MBSR (n=145), or (2) SME control (n=145). Subjects will then undergo study visits again at 2 months (after Class #8/after the standard 8-week MBSR or SME program) and at 6 months (after Booster session #4/end of study), where the baseline procedures and measures will be repeated.

During the study, all subjects will continue to receive usual care from their physicians and will be advised not to change or discontinue any of their medications during the study unless directed to do so by their physician. As these subjects have uncontrolled diabetes, it is expected that they will be on medical treatment as prescribed by their physician, and they will be advised to follow-up with their physician every 3 months to ensure they are on optimal medical treatment. During the study, all subjects will be encouraged to continue their routine activities and they will be asked not to take part in any other formal stress reduction programs.

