### **8.2 Sample size determination**

The primary outcome for this trial is the absolute difference between the two interventions with respect to the mean change in hemoglobin A1c from baseline to month 6 and we consider an absolute difference of 0.5% in this outcome to be clinically meaningful. As this is an individually randomized group treatment trial, correlation among observations within groups (defined here as class cohort), as measured by the intraclass correlation coefficient (ICC), must be taken into consideration (Pals et al., 2008). The variance inflation factor, or design effect, for this type of trial will inflate the sample size by  $1+(1-m)p$ , where  $m$  is the average group size and  $p$  is estimated by the ICC. For both interventions (MSBR and SME), we plan to have the average group size be 18 subjects and expect the ICC=0.08. Thus, the design effect is 2.36. Furthermore, we anticipate that 15% of the subjects will drop-out of the study prior to completion. Incorporating the design effect of 2.36 and the anticipated 15% drop-out, a sample size of 290 subjects (145/intervention) will provide 80% power to detect a clinically meaningful 0.5% absolute difference between the two interventions with respect to the mean change in hemoglobin A1c from baseline to month 6, assuming a standard deviation of 0.9% (Frias et al., 2011) using a two-sided test having a significance level of 0.05.

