### **8.3 Statistical methods**

Data (i.e., physiologic, behavioral, diabetes-related distress, and mindfulness) will be collected longitudinally in this trial. The time period of primary interest in this trial is the change from baseline to

6-months. Linear mixed effects models, which are subject-specific models, will be fit and contrasts constructed to assess adjusted changes from baseline between interventions over time with respect to these continuous outcomes (e.g., the primary outcome of hemoglobin A1c). The primary contrast of interest is the change in an outcome from baseline to month 6 between the two interventions. However, contrasts will also be constructed to assess the change in an outcome from baseline to other points in time (e.g., month 2) between the two interventions to gauge, for example, if the intervention is effective at month 2. The independent fixed factors for the mixed-effects models will include intervention, time (e.g., baseline, 2 months, 6 months), the randomization stratification factor of insulin vs. non-insulin treated at baseline, and the interaction of intervention with time. The group (class cohort) the participant is assigned will be a nested random effect (i.e., group/class cohort will be nested within intervention) in the mixed-effects models to account for the correlation among observations within groups (class cohorts) inherent in an individually randomized group treatment trial (Pals et al., 2008; Murray et al., 2004). Each class cohort will be characterized by various class sizes, instructors, etc. and thus will be important to account for throughout the duration of the trial wherever possible. The time factor in the models for the vast majority of the outcomes will consist of measurements taken at baseline, 2 months, and 6 months, per subject. An unstructured variance-covariance matrix will be pursued to assess the residual error associated with the repeated measurements over time per participant. If this variance-covariance structure fails to provide model convergence, then others will be explored. Linear mixed-effects models are an extension of ordinary regression models that account for the between- and within-subject correlation inherent in longitudinal trials. Mixed-effects models also appropriately handle the correlation within groups for individually randomized group treatment trials by specifying these groups as random effects. Residual diagnostics will be used to determine the appropriateness of model fit and, if necessary, transformations (e.g., logarithmic) of the outcome will be performed to meet modeling assumptions. If transformations fail to provide adequate model fit then adding splines to the linear mixed-effects models, or using nonlinear mixed-effects models, will be considered.

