
Following our assessment of the initial fit of the models, we will add covariates to the models to assess their impact, if any, on the intervention outcome effects. Some of the covariates to potentially be considered at baseline include biological sex, age, BMI, race, ethnicity, education, income, Adverse Childhood Experiences (ACEs), trial expectations/reasons for joining the trial, marital status, work status, type of diabetes, number of years with diagnosed diabetes and whether insulin-treated or non-insulin treated. We will also explore potential effects of diabetes-related medication changes that took place during the trial that could have impacted the outcome measure at-hand (and/or self-reported adherence to prescribed diabetes medications). As many diabetes patients take medications to lower their HbA1c, this will be an important factor to control for during analysis.

We will follow the principle of intention-to-treat for all primary analyses. In other words, we will include the data on each randomized participant in the statistical analyses, regardless of whether that participant was fully engaged in the study (e.g. participants who were randomized and withdrew prior to starting their randomized allocation, participants who remained active in the study but were not fully compliant in attending their randomized allocation study sessions, level of home practice engagement, etc.). Secondary analyses may explore subgroups of subjects with higher engagement and/or compliance with their study sessions (e.g. subjects who attended at least 8 out of the first 10 sessions). We may use the observed data to determine if/how participants who completed the study differed from those who did not. Statistical methods to account for differential dropout will be considered, if applicable.

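### As written, the class random effect in section 8.3 cancels from the baseline-to-month-6 contrast, so the primary test ignores the clustering that section 8.2 pays for

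*Combined protocol and SAP*

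**What the plan says.** Section 8.3 sets out a linear mixed model with all three visits in the outcome: "The independent fixed factors for the mixed-effects models will include intervention, time (e.g., baseline, 2 months, 6 months". The other fixed terms are the insulin stratum and the intervention-by-time interaction. The target is stated: "The primary contrast of interest is the change in an outcome from baseline to month 6 between the two interventions".

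Clustering enters through one term: "The group (class cohort) the participant is assigned will be a nested random effect (i.e., group/class cohort will be nested within intervention". The other covariance statement concerns the individual participant: "An unstructured variance-covariance matrix will be pursued to assess the residual error associated with the repeated measurements over time per participant". Section 8.3 says that the class term is there to handle correlation within class cohorts. It does not say whether the class effect may differ between visits, and it names neither a class-by-time term nor a degrees-of-freedom method.

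Section 8.2 takes an average class size of 18 and an ICC of 0.08 and concludes: "Thus, the design effect is 2.36". It applies that factor to the change in HbA1c from baseline to month 6, with an SD of 0.9%.

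**The concern.** A class intercept is a constant added to every visit of every member of a class. Subtracting baseline from month 6 removes it. The unstructured residual matrix cannot replace it, because that matrix links the visits of one person and not different people in one class.

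The baseline visit comes before randomization and before any class meets (sections 7.2.2 and 7.2.4). Whatever a shared class and instructor do to HbA1c can therefore appear only in the change, which is the part this model leaves unclustered.

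At stake are the standard error, confidence interval and p-value of the only primary contrast. The error is towards false positives. The sample size was more than doubled for clustering that the test would then leave out.

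**Working it through.** **Inputs.** From section 8.2: difference 0.5, SD of change 0.9, two-sided 0.05, 80% power, 18 per class, ICC 0.08, drop-out 15%, 145 per arm. From section 4.2.3: cumulative randomization of 36, 72, 120, 174, 230 and 290 by months 30, 36, 42, 48, 54 and 60 ("We expect to reach this target by randomizing 36 subjects by month 30, 72 subjects by month 36, 120 subjects by month 42" is the first part). From section 7.2.4: "We will run a new cohort of MBSR and SME control classes approximately every 3 months".

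**1. The plan's own figure.** A two-sample t-test needs 51.84, so 52 per arm. The design effect is 1 + (18 − 1) × 0.08 = 2.36. Then 52 × 2.36 = 122.72, and 122.72/0.85 = 144.4, so 145 per arm and 290 in all. This reproduces section 8.2. (The formula printed there, with 1 − m in place of m − 1, would give −0.36. It is a sign slip without effect on the result.)

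**2. Cancellation.** With visit contrast c = (−1, 0, 1) and class-intercept variance σ², the class contribution to the variance of the contrast is σ²·c′11′c = σ²·(−1 + 0 + 1)² = 0. REML fits to complete simulated data agree. The estimated contrast equals the raw difference in mean change to about 1e-14, also with unequal classes. The model SE is 0.104–0.105, against 0.9 × √(2/145) = 0.106 with no clustering.

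**3. Class sizes implied by accrual.** The six-month increments are 36, 36, 48, 54, 56 and 60, if the first 36 also take six months. Two waves per six months and one class per arm per wave mean division by 4: 9, 9, 12, 13.5, 14 and 15 per class. The mean is 290/24 = 12.1 randomized, or 10.3 after 15% drop-out.

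**4. Type I error.** The true variance is 2·SD²·DE/n, and the model uses DE = 1. The rejection rate under the null is 2·(1 − Φ(1.96/√DE)), with DE = 1 + (m − 1)·ICC. At ICC 0.08:

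| Per class (m) | DE | Type I error |
|---|---|---|
| 7.65 (9 less 15%) | 1.532 | 11.3% |
| 9 | 1.640 | 12.6% |
| 12.1 | 1.886 | 15.4% |
| 12.75 (15 less 15%) | 1.940 | 15.9% |
| 15 | 2.120 | 17.8% |
| 15.3 (18 less 15%) | 2.144 | 18.1% |
| 18 | 2.360 | 20.2% |

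A 40,000-run check on complete data gave 12.6%, 17.6% and 20.2% at 9, 15 and 18 per class.

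**5. Sensitivity.**
- ICC 0.01–0.02: 5.9–8.3% at 9–15 per class and 7.0–9.0% at 18.
- ICC 0: 5%.
- If half of the 0.08 is a calendar effect shared by the concurrent classes of the two arms, that half cancels between arms and DE = 0.92 + 0.04m. The rates are 8.3% (m = 9), 11.2% (m = 15) and 12.6% (m = 18).

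**6. Simulation with drop-out.** REML, 1,000 null trials per row, 15% missing both follow-ups with baseline rows kept. Assumptions not in the documents: visit SD 1.2, month-2 class effect 0.7 of that at month 6, drop-out at random. Monte Carlo SE is about 1 point for the inflated rates.

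| Scenario | Intercept model, z | Intercept model, class-based df | Class-by-time, class-based df |
|---|---|---|---|
| ICC 0.08, 24 classes of 9–15 | 14.6% | 13.2% | 6.2% |
| ICC 0.08, 16 classes of 18 | 21.3% | 16.9% | 6.1% |
| ICC 0.02, 16 classes of 18 | 6.8% | 4.8% | 2.5% |

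In the first row the intercept model reports an SE of 0.113 against a true 0.152; in the second, 0.113 against 0.172. A separate simulation with 16 classes of 15 at ICC 0.08 gave 18.3% for the intercept model and 4.7% for class-by-time with class-based df.

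**7. Power with class-based df** (noncentral t, 145 × 0.85 = 123.25 completers per arm).
- 16 classes of 15.3 completers: DE 2.144, SE = 0.9 × √(2 × 2.144/123.25) = 0.168, noncentrality 2.98, 14 df, power 79%.
- 24 classes of 10.3 completers: DE 1.742, noncentrality 3.31, 22 df, power 88%.
- 24 classes, with DE 1.886 from the 12.1 randomized per class: power 86%.

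**The case against.** The strongest reply is that section 8.3 never says random intercept. It calls class a nested random effect, gives its purpose as handling within-class correlation, and says class should be accounted for through the trial where possible. A class effect that varies by visit is compatible with that. This stands in part: the authors may have meant it. But no such term is named anywhere, and the literal specification is an intercept.

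The size is conditional. The ICC of 0.08 is a planning value with no source of its own, and 9–15 per class is derived, whereas section 8.2 states 18. A lower ICC, a calendar effect shared between arms, or counting completers only all reduce the inflation, as shown. At ICC 0.02, class-based degrees of freedom alone bring the intercept model to 4.8%. These points stand as limits on the size. They do not remove the defect at the plan's own ICC, where class-based df still leave 13.2–16.9%.

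The remedy has a price. Where the class effect is constant over visits, the intercept model is about right (3.8–4.8% in 400-run simulations, 16 classes of 15) and the class-by-time model is conservative (0.8–2.5%). That is the cost of a near-zero ICC in the change. Keeping a class intercept as well hardly alters it (SE 0.125 against 0.127).

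**Conclusion.** The point holds. Fitted as written, section 8.3 gives the primary contrast a standard error without the clustering that section 8.2 assumes for the same quantity. At the plan's ICC of 0.08, type I error is about 13–18% for classes of 9–15 randomized, about 11–16% counting completers, and about 20% at the stated 18. It falls to 6–8% at an ICC of 0.01–0.02 with 9–15 per class, and to 5% if the change has no class correlation.

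The cancellation is exact with complete data. With drop-out it rests on simulation, in which the inflation remained. The rates assume class variation in the change and, for 9–15 per class, one class per arm about every three months. This should be settled before unblinding, because a later choice of random-effects structure could change the conclusion.

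**What to change.** In section 8.3, state that class, nested in intervention, enters as a class-by-time random effect with class-specific effects at months 2 and 6. Test the month-6 contrast with class-based degrees of freedom, for example Kenward-Roger, about 2(k − 1) for k classes per arm.

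Name an ordered fallback if the 2 × 2 class covariance does not converge:
1. one common class variance for the follow-up visits;
2. a class random effect on the month-6 change;
3. a class-level t-test of mean change.

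Fallbacks 2 and 3 use month-6 completers only. They therefore depart from the commitment in section 8.3 that "we will include the data on each randomized participant in the statistical analyses", and the plan should say so. A model of months 2 and 6 with baseline HbA1c as covariate is an alternative but not an equivalent, because it drops participants with no follow-up.

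Restate power with class-based degrees of freedom: about 79% for 16 classes and 86–88% for 24.

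The cost is SAP wording and a changed model, with no new data or patients. Intervals become wider, as the sample size already assumed. The class covariance must be estimated from about 16–24 classes, so non-convergence is possible. At a small ICC the test is conservative (2.5% at ICC 0.02 with 16 classes). The term does not capture an instructor effect shared by several classes of one arm.

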#### Method to Assess Potential Mediating Effects

For the primary outcome of hemoglobin A1c, we want to ensure that potential mediators (e.g. stress) are considered so that the effect of the MBSR intervention on the primary outcome is appropriately

estimated. Various measures of stress (and other potential mediators) are collected throughout the study longitudinally using questionnaires and surveys at each of the study visits (Baseline, 2MO, 6MO). Using the generalized linear regression methods presented by VanderWeele (2014), the overall effect on the primary outcome of the change in hemoglobin A1c will be decomposed into 4 components: (1) the controlled direct effect (CDE) due to MBSR intervention, (2) the reference interaction (IRF) between the MBSR intervention and the mediator, (3) the mediated interaction (IMD) between the MBSR intervention and the mediator, and (4) the pure indirect effect (PIE) due to the mediator. Dividing each of these components by the total effect provides the corresponding proportion contributions of these components. These 4 components will provide insight into how much of the total overall effect is: (a) due to neither mediation nor interaction (i.e., CDE), (b) due to interaction (i.e., IRF), (c) due to both mediation and interaction (i.e., IMD), and (d) due to mediation (i.e., PIE). Other potential mediators of the primary outcome will be assessed similarly, and additional exploratory subgroup analyses may be performed to explore these potentially mediating effects whenever necessary. The plan is to use SAS PROC CAUSALMED.

All hypothesis tests will be two-sided and we will invoke a 0.05 two-sided significance level for all primary and secondary statistical analyses. As our analyses are based upon defined hypotheses, we have not included corrections for multiple testing. While the issue of p-value adjustment for multiple testing has long been a topic of discussion in observational epidemiology and clinical trials, it generally is accepted that p-values should not be the sole criterion for assessing relationships. Conclusions will be based on the preponderance of scientific evidence related to each hypothesis, considering point estimates and confidence intervals, as well as statistical significance. Nonetheless, findings with marginal statistical significance will be interpreted cautiously, taking into consideration a type I error. Further, we deem that interim statistical analyses are not necessary for this trial, so we will not pursue such analyses. All analyses will be performed using SAS software, version 9.4 (SAS Institute, Inc., Cary, NC), R software, version 3.5.1 (R Foundation for Statistical Computing, Vienna, Austria), or Stata software, version 13 (StataCorp LP, College Station, TX).

## **9.0 Data and Safety Monitoring Plan**

### **9.1 Periodic evaluation of data**

Interim statistical analyses of primary and secondary outcomes are not necessary for this trial and will not be performed.

### **9.2 Data that are reviewed**

Recruitment, enrollment, retention, demographics, subject status, adherence to study intervention, patient-reported safety assessments and Adverse Events data will be reviewed. See Data and Safety Monitoring Plan in Appendix.

### **9.3 Method of collection of safety information**

For this study, we adapted recent recommendations and resources provided by [name], an external consultant with expertise in the adverse effects of mindfulness-based interventions, and updated the adverse event (AE) collection and reporting methods, and the CRFs for tracking and tabulating adverse events, that we used in our previous NIH-funded mindfulness study. Additionally, [name] recently updated the National Center for Complementary and Integrative Health (NCCIH) DSMP template v.3.0 to meet CONSORT Harms Criteria, which we used as a guide to update our DSMP (Ioannidis et al., 2004).

Adverse events will be recorded at each study visit (the baseline study visit, follow-up phone call after Class #4, 2-month study visit, and 6-month study visit) and throughout the study whenever subjects or their instructors initiate reporting of an adverse event. Within 24 hours, adverse events in participants assigned to MBSR will be reported via phone or email by [name] from West Chester University (or other study MBSR instructor e.g. [name]) to the SME instructors to maintain blinding. Within 24 hours, adverse events in all participants (MBSR and SME) will be reported via phone or email by the SME instructor to the blinded research coordinator and the overall study PI [name] at the primary site at Hershey. The SME instructor will communicate adverse events (e.g. requiring a change in MBSR or SME practice recommendations), and other information about MBSR subjects and SME subjects, to the blinded research coordinator and to [name] in a manner that does not reveal which instructor the subject reported the adverse event to, or any other information that would reveal the subject's group assignment. To accomplish this, we will minimize the 'discussion' aspect of how the SME instructors report the AE, or any other information about a subject, to the research coordinator because discussion of the report may lead to unblinding/may make it obvious as to which instructor it was reported to if the SME instructor doesn't know much about the encounter. The SME instructor will simply state e.g. "Participant ID 123 has reported  to an instructor." The research coordinator will then follow up with the subject via phone for formal AE documentation. If indicated, the research coordinator will complete an Adverse Event form.

All subjects will be followed up to 6 months. Adverse events will be followed for outcome information until resolution or stabilization. Adverse events will also be entered in the REDCap database.

Adverse Event Forms will be completed for each adverse event that a subject experiences (See Data and Safety Monitoring Plan in Appendix). Severity and expectedness will be determined using a specific set of external criteria provided by [name] who is independent from the study team and does not have a conflict of interest (See Severity Grading Tool and [name] of Previously-Reported Meditation Effects). These external criteria include precise definitions for severity and expectedness. The descriptions and grading scales found in the revised NCI Common Terminology Criteria for Adverse Events (CTCAE) version 5.0 will also be utilized for AE reporting ([http://ctep.cancer.gov/protocolDevelopment/electronic\\_applications/ctc.htm](http://ctep.cancer.gov/protocolDevelopment/electronic_applications/ctc.htm)). We will use [name] of Previously-Reported Meditation Effects to determine whether the symptom is an expected effect, and to determine the symptom Domain out of 8 domains including a Diabetes Domain in addition to [name] 7 domains (Affective, Cognitive, Conative, Perceptual, Sense of Self, Social, and Somatic). This is in-line with CONSORT harms guidelines as it improves precision and reduces subjectivity around the assessment of severity and expectedness.

Furthermore, the Stress Experience Survey which includes questions about the most common meditation-related symptoms and other stress-related symptoms, will be administered by the research coordinator at the baseline study visit, follow-up phone call after Class #4, 2-month study visit, and 6-month study visit. Additionally to allow for corrective feedback during the MBSR course, subjects will be sent a link from REDCap to complete a Midway Check-in questionnaire after Class #5 so that instructors can adjust mindfulness practice recommendations when indicated based on subjects' responses.

The research coordinator will administer a Hypoglycemia Survey at the baseline study visit, follow-up phone call after Class #4, 2-month study visit, and 6-month study visit. The Hypoglycemia Survey will ask about self-reports of Level 2 hypoglycemia (glucose < 54 mg/dL) and Level 3 hypoglycemia (hypoglycemia requiring the assistance of another person for treatment). Level 2 hypoglycemia will be recorded as an Adverse Event. Level 3 hypoglycemia will be recorded as a Serious Adverse Event (see DSMP).

The Principal Investigator will confirm that all adverse events (AE) are correctly entered into the AE case report forms by the coordinator; be available to answer any questions that the coordinators may have concerning AEs; and will notify the IRB, NIH, CRC/CTSI and DSMB of all applicable AEs as appropriate. All assessments of AEs will be made by a licensed medical professional who is an investigator on the research team.

The Research Coordinator will complete the appropriate report form and logs; assist the PI to prepare reports and notify the IRB, NIH, CRC/CTSI and DSMB of all Unanticipated Problems/Serious Adverse Events (SAEs). See Data and Safety Monitoring Plan in Appendix.

